In summary, suicide rates in Veterans continue to be unacceptably high and existing treatments only reduce risk to a moderate degree but do not eliminate it. Furthermore, not all patients respond to standard psychotherapy treatments. Patients with severe depression and those with comorbid personality pathology tend to show smaller gains in symptom reduction after CBT than those with moderate-mild symptoms and no comorbid personality pathology. Unfortunately, those with severe symptoms are at significantly higher risk of dying by suicide. Consequently, finding ways to augment the effect existing treatments is critical. TMS is an ideal treatment to add to brief cognitive behavioral therapy for suicide. It targets the same neurobiological mechanisms, it improves the types of executive functioning ability required for learning and retaining CBT skills, it is being rolled out at VAMCs across the country, and it may be a more acceptable treatment than pharmacotherapy. No studies have examined whether adding TMS to standard brief cognitive therapy increases the suicide prevention effect of BCBT therefore, we propose to examine whether combined TMS + BCBT enhances treatment outcomes. Importantly, by including MRI into the design of this study, we now have the methodological means to discover etiologically-relevant patterns brain function and treatment response.

C. PRELIMINARY

STUDIES C1. Pilot BCBT

Data:

Co-Investigator [name] has trained, supervised and conducted research utilizing Cognitive Behavioral Therapy for 30+ years, including multiple clinical trials involving cognitive therapy for severely depressed and suicidal inpatients [44-47]. MPI [name] is a clinical psychologist, national expert in suicide prevention, and has worked closely with Dr.

[name] on several clinical trials. [name] co-developed the BCBT protocol that will be used in this study [19] and may provide consultation on therapist training and assessment of treatment fidelity.

C2. Pilot TMS Data:

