D2.2 Feasibility of enrolling targets: The enrollment, recruitment, and inclusion/exclusion criteria used in this study were modeled after procedures used by [name] in her PVAMC IRB-approved study “Veterans Coping Long Term with Active Suicide.” [name] staff screened 168 potential patients from the PVAMC inpatient unit ultimately enrolling 100 participants in 3.5 years of active enrollment. In her study, thirty-five (21%) of screened individuals were excluded for with borderline personality disorder which is not exclusionary for this study. We expect that ~20% of potential participants will have an MRI contraindication based on exclusion rates from PVAMC IRB-approved studies (PI: [name].). Enrollment targets are feasible, especially given the longer 5-year timeline of this study.

D3. Pre-screening, Recruitment, & Informed Consent

D3.1 Identification and Pre-Screening of Potential Participants: Pre-screening allows for the identification of a rare, low base rate study population. Pre-screening will also allow us to identify potential diagnosis, sex, and age matched Veteran controls while minimizing the number of screens reducing burden for potential participants. We will administer MRI and TMS safety questions verbally to interested potential participants during either in-person or telephone pre-screening to limit burden of completing informed consent for individuals that cannot be scanned or stimulated safely (e.g. shrapnel not reported in medical record, history of metal-work without proper protective gear, permanent makeup). Please see questionnaires for additional information.

D3.1.1 Pre-Screening of Potential Participants with STBs.

A HIPAA waiver will be obtained for screening purposes. Veterans will be recruited from the psychiatric inpatient units or outpatient care at the Providence VAMC through three primary strategies:

- 1)**Chart reviews:** Research staff will screen charts daily for patients newly admitted to the inpatient unit for suicidality. Identified charts will be screened for MRI and/or TMS contraindications (e.g. pacemakers) and other medical exclusionary criteria.
- 2)**Suicide Prevention Coordinator (SPC) referrals:** Research study staff will also check -in with the local SPC or SPC staff bi-weekly to identify potential study participants.

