All assessments will be conducted by trained interviewers and will be supervised by study Co- PIs. Our training procedures consist of: a) review of relevant written materials, b) didactic instruction from senior staff and experienced interviewers, c) practice interviews with review, feedback and reliability ratings from senior staff and experienced interviewers and d) continued practice, training and feedback until high agreement with established consensus ratings are met (e.g. three consecutive C-SSRS ratings are within 2 points of our consensus ratings). Additionally, all interviewers will be certified on the C-SSRS using established training procedures. Following initial training, all interviewers and senior staff will meet to review any questions/issues as needed.

Assessment	Collected At:
Demographics, Safety, and History	
Demographics	BL
TMS Safety Form	BL
MRI Safety Form	BL
Treatment History	BL
Treatment Utilization (chart review)	BL, EP, F/U
Treatment History Interview (THI)	EP, F/U
TBS Blinding Assessment	EP
Diagnosis and Cognitive Impairment	
Montreal Cognitive Assessment (MoCA)	BL**
Structured Clinical Interview for DSM-V (SCID-V)	BL
McLean Screen for Borderline Personality Disorder (MSBPD)	BL
Alcohol Use Disorders Identification Test (AUDIT)	BL, EP, F/U
Drug Use Disorders Identification Test (DUDIT)	BL, EP, F/U
Suicidal Thoughts and Behaviors	
Columbia Suicidal Severity Rating Scale (C-SSRS), including Military- Specific Risk Assessment Questions	BL, EP, F/U
PhenX Beck Scale for Suicide Ideation (SSI)	BL, I^, F/U*
PhenX Self-Injurious Thoughts and Behaviors Interview (SITBI, Items 51-72)	BL**, EP, F/U
Longitudinal Interval Follow-Up Evaluation (L.I.F.E.) - sections: suicidal ideation and behavior	EP, F/U
Beck Hopelessness Scale (BHS)	BL, EP, F/U
Brief Symptom Inventory (BSI)	BL**, EP, F/U
Trauma	
PTSD Checklist (PCL-5)	BL, I, EP, F/U
Childhood Trauma Questionnaire (CTQ)	BL**
Deployment Risk and Resilience Inventory (DRRI, Sexual Harassment, Combat Subscales)	BL**
Depression and Anxiety	
Inventory of Depressive Symptomatology (IDS-SR)	BL, I, EP, F/U
Depression, Anxiety, and Stress Scale (DASS)	BL**, F/U
World Health Organization Disability Assessment Scale 2.0 (WHODAS 2.0)	BL**, EP, F/U
Sleep	
Pittsburgh Sleep Quality Index (PQSI)	BL**, F/U
Impulsivity	
PhenX UPPS Impulsive Behavior Scale	BL**
The Barratt Impulsiveness Scale (BIS-11)	BL**

Table 2. Assessment battery.

BL = Baseline visit

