We will use the urn randomization strategy and ensure balance among treatment groups [67,68]. We have successfully used urn randomization in previous treatment studies [44, 69] and developed a computer program that conducts the randomization. Urn randomization is a biased coin randomization technique, which randomly assigns Veterans of a given subgroup to treatment conditions (i.e., active TMS+BCBT or sham TMS+BCBT) while systematically biasing randomization in favor of balance among the treatment conditions on select variables. This program enables ongoing monitoring of the effectiveness of our stratification and randomization procedures. Since the number of variables which can be successfully balanced is limited, for the current study we will include the following variables in our randomization: a) current

admission due to suicide attempt vs. suicide risk, b) number of previous suicide attempts (none, single vs. multiple), and c) gender (male vs. female).

D4.4.2 BCBT Procedures: Participants will receive a standard course of BCBT (12 weekly individual therapy sessions). These sessions will be completed in-person at the Providence VAMC. In rare circumstances (e.g., pandemic, extreme weather), these sessions may be provided via phone or video (VA approved VA Video Connect). When therapy sessions are conducted remotely, de-identified data may be collected by study staff at home due to remote

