Preliminary analyses will include descriptive statistics to examine the distributional and psychometric properties of the variables (e.g., normality, internal consistency). Variables will be transformed to achieve normality if necessary. We will also examine post-inclusion attrition by comparing study completers to dropouts on sociodemographic, baseline, and length of admission data to determine if they differ systematically. Preliminary analyses may also include analyses of adverse events, progress of recruitment and retention, and quality markers as the study progresses. In keeping with the intention to treat principle, missing data will be handled with multiple imputations (m=20) with assumptions checked with sensitivity analyses [43,44] [32]. Our main analysis will not adjust for covariates other than baseline value of the outcome and design factors (balancing factors used in the urn randomization procedure) under the assumption that randomization produced groups balanced on measured and unmeasured confounders. Additionally, the data from this study across all Aims will be combined with data from subjects who completed neuroimaging procedures in PVAMC IRB protocol #2018-051.

Data from this study, across all Aims, will also be combined with data from subjects who completed procedures for PVAMC IRB protocol #IRB-2020-008. Data from this study related to recorded interviews, de-identified with the exception of assessment dates, will also be shared with the PVAMC research study “Longitudinal Assessment of the Sleep-Suicide Link in Veterans Discharged from Inpatient Psychiatric Care” (IRB-2020-008), for training of staff and inter-rater reliability analysis (i.e., to calculate agreement across interviewers and to make final decisions on ratings).

E2. Aim 1 Analytical Plan (Analyses Related to Treatment)

The data from this study for Aim 1 may be combined with data from subjects who completed neuroimaging procedures in PVAMC IRB protocol #2018-051. Data from this study, for Aim 1 may also be combined with data from subjects who completed procedures for PVAMC IRB protocol #IRB-2020-008.

E2.1 Interim analysis and early stopping of treatment

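### The main analysis omits baseline depression severity and the borderline screen, two collected predictors the protocol itself points to, because randomisation is assumed to balance the arms; some precision may be forgone

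*Combined protocol and SAP*

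**What the plan says.** Section B6 states that "Patients with severe depression and those with comorbid personality pathology tend to show smaller gains in symptom reduction after CBT", and adds that "those with severe symptoms are at significantly higher risk of dying by suicide". Under D4.4 every randomised participant receives BCBT, so on the protocol's own account these traits bear on response in both arms.

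D2.2 reports that in the site's model study "thirty-five (21%) of screened individuals were excluded for with borderline personality disorder which is not exclusionary for this study". Table 2 schedules the IDS-SR and the MSBPD at the baseline visit, and neither carries the mark that lets a measure be deferred to the next appointment.

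The urn factors in D4.4.1b are admission for attempt versus risk, number of previous attempts (three levels) and gender. Neither trait is among them.

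E1.1 then sets the covariate rule: "Our main analysis will not adjust for covariates other than baseline value of the outcome and design factors". The reason given is "under the assumption that randomization produced groups balanced on measured and unmeasured confounders". The primary model in E2.2 follows this rule, and no covariate-adjusted sensitivity analysis of the primary outcome is planned. Diagnosis and comorbidity reappear only as exploratory moderators in E2.4.

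**The concern.** The reason given does not support the restriction. Randomisation makes covariates balanced in expectation, which protects the estimate from systematic error. Adjustment for a prognostic covariate does a different job: it removes outcome variance that would otherwise sit in the residual, and it conditions on whatever chance difference has arisen. Both benefits are available in a perfectly conducted randomised trial.

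The plan accepts this logic elsewhere. E2.2.1 credits ANCOVA with a smaller detectable effect because of the baseline outcome, but assumes r = .2, so that covariate explains only 0.2² = 4% of the variance. The other 96% is left to the urn factors and to noise. With about 65 per arm, two already collected variables that the background section singles out are the natural candidates to explain some of it. If a visible imbalance in either appears after unblinding, the plan has no pre-specified response, and any adjustment made then would be post hoc.

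**Working it through.** **Inputs.** n = 65 per arm (E1). Detectable effect √(16/n), or √(16(1−r²)/n) with ANCOVA, and r = .2 (E2.2.1). Borderline frequency 35/168 = 21% of those screened in the model study (D2.2). The share of residual variance that the two covariates would explain, R², is not in the documents and is an assumption throughout.

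**The plan's figures first.**
- Unadjusted: √(16/65) = 0.496, which agrees with the stated 0.50.
- With r = .2: √(16 × 0.96/65) = 0.486. The plan prints .47, which its formula does not give; .47 would need r = √(1 − 0.47² × 65/16) = 0.32. The comparison below starts from 0.486.

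**Adding the two covariates.** Residual variance v = 0.96 × (1 − R²); detectable d = √(16v/65); power at d = .47 is Φ(0.47/√(2v/65) − 1.96), two-sided 5%. Equivalent extra patients = 130/(1 − R²) − 130.

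| Assumed R² | Detectable d | Power at .47 | Equivalent extra patients (total) |
|---|---|---|---|
| 0 | 0.486 | 78.1% | 0 |
| 0.02 | 0.481 | 78.9% | 2.7 |
| 0.05 | 0.474 | 80.1% | 6.8 |
| 0.10 | 0.461 | 82.2% | 14.4 |

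**Cost of two parameters.** With a rough allowance for two residual degrees of freedom (variance factor 126/124), detectable d at R² = 0 moves from 0.486 to 0.490, a loss of about 0.004. The net values are 0.485, 0.478 and 0.465 at R² = 0.02, 0.05 and 0.10. Break-even is near R² = 1 − 124/126 = 1.6%.

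**Simulation check.** Linear ANCOVA with 130 patients, one continuous covariate and one binary covariate at 21%, 4,000 runs per setting: power at d = .47 went from 77.0% to 78.5% at R² = 0.05 and from 77.0% to 80.8% at R² = 0.10. At R² = 0 it did not rise (77.2% and 76.8%). Type I error stayed near 5% with or without the covariates.

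**Chance imbalance.** The standardised difference in an unbalanced covariate has SD √(2/65) = 0.175, so a 95% range of ±0.34. If its correlation with the outcome were 0.2 to 0.3 (assumed), the unadjusted estimate would move by up to 0.34 × 0.2 = 0.07 to 0.34 × 0.3 = 0.10 SD. At 21% prevalence the arms differ by 10 points or more with probability about 16%. This variation is already counted in the standard error.

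**Why the Cox model is different.** On the E2.2.1 figures, expected first attempts are 65 × 0.21 + 65 × 0.045 = 13.65 + 2.93, about 17. Treatment, four urn parameters (1 + 2 + 1) and two further covariates make seven, or 16.6/7 = 2.4 events per parameter.

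**The case against.** The strongest reply is that the documents do not show either variable to be prognostic for this outcome. B6 speaks of gains in symptom reduction, whereas the primary outcome is a C-SSRS total of suicidal behaviours. The link from severe symptoms to suicide death is given without a size, and none is given for personality pathology. Section B5.3 says that models built on a few individual risk factors have predicted suicide no better than chance. The pilot correlation between depressive and suicide-item change (C2) concerns changes, not baseline prognosis. All of this stands, and it is why the gain is shown as an assumed range that includes almost nothing.

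Second, the planned model is not the baseline composite alone. It includes previous attempts and index event, and the Aim 2 design considerations lean on previous attempt as a strong risk factor. This also stands. The 0.486 starting point gives the urn factors no explained variance, so R² must be read as what the two covariates add beyond them.

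Third, a short pre-specified list tied to the randomisation factors is a legitimate choice. It is. A reader might infer that the planned analysis is biased, or that an imbalance in borderline disorder would invalidate it. Neither follows: chance imbalance is random error already reflected in the standard error, and type I error is unaffected. A reader might also infer that strong predictors are being discarded; the documents do not establish that strength.

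Two measurement limits remain. The MSBPD screens for borderline disorder only. The 21% comes from screening on an inpatient unit, while this trial also recruits outpatients.

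**Conclusion.** The point holds as a missed efficiency. Assumed balance is not a sound reason to exclude covariates that the protocol itself links to CBT response, that are already collected at baseline, and that the urn does not balance. The primary analysis remains valid without them.

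The plausible benefit is modest. Detectable d falls from 0.486 to about 0.47 or 0.46 if the covariates explain a further 5% or 10% of residual variance beyond the baseline composite and the urn factors, and it is close to unchanged at 2%. These figures use the plan's continuous-outcome approximation; a sparse count of suicidal behaviours could behave differently. The premise applies most directly to the secondary symptom and functioning scores, where B6's statement about symptom reduction is closest to the outcome. This is a cheap improvement worth making, not a correction that the trial's validity depends on.

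**What to change.** Before the interim look at 32 per group, amend E1.1 and E2.2, and the WHODAS and C-SSRS ideation mixed models in E2.3, to read along these lines: models adjust for the baseline value of the outcome, the urn factors, baseline IDS-SR total and baseline MSBPD score. Drop the balance argument as the justification for the covariate list.

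State which IDS-SR counts as baseline. D4.4 has it readministered when treatment starts more than two weeks after the baseline visit, so two values can exist; the one used should precede randomisation.

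Report the currently planned model, without the two covariates, as a sensitivity analysis. Do not add them to the Cox model for time to first attempt.

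Cost: a few sentences in the plan and no new data. There are two more parameters with 130 Veterans, worth about 0.004 in detectable d, and little or no return if the covariates prove weakly prognostic.

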This task identifies brain areas involved in processing rewards and expected values. [54,55]. The task is divided into two, 48 trial, 7-minute scanner runs (Figure 2). On each trial, participants virtually “bet” via button press whether the number on the next card displayed (range=1-9) will be higher or lower than 5 (guess (?) phase). Next, an expectancy card is shown communicating the likelihood that the bet will result in a win, a loss, no change, or win/loss equally likely (cue phase). The number is then shown (# phase), followed by the win/loss amount (feedback phase). Expectancy cues are accurate on 50% of trials (except for neutral trials) producing neural “prediction errors” on misleading cue trials. Trials are separated by a 0.5-1.5s jittered inter-trial interval. Trial order is randomized with 12 trials per category (win, loss, neutral, ambiguous).

[figure not shown]

Fig. 2 The reward expectancy card guessing task⁵⁴ On each trial, participants guess (?) whether the number on a later card (#) is higher or lower than 5. An intervening cue card (Cue) sets an outcome expectancy. Feedback (\$) after the card reveal corresponds to wins, losses, or a push. The difference between the actual outcome - win, loss, or push ("\$") - and the expected value is the prediction error.

III. Stop-signal reaction time task (SSRT)

The SSRT measures inhibitory cognitive control [57,58] The task is divided into two, 128 trial scanner runs. On each trial, participants indicate whether a visually-presented ‘go’ arrow stimulus points to the left or right (50/50% probability) using a MRI-safe button box. During 25% of trials (random assignment), a stop-signal (up arrow) indicating that responses are to be withheld is delivered at a delay after the go arrow. On stop trials, the delay between the go cue and the stop signal is the ‘stop-signal delay’ (SSD). The SSD is varied based on performance[58]. Null events ranging from 0.5 and 4 s (mean, 1 s) will be interspersed between trials.

D4.4 Intervention [(active or sham) TMS +BCBT]

If eligible and willing to participate in the intervention, participants will be scheduled for the start of TMS+BCBT as soon as scheduling allows following the baseline visit and following their first MRI visit (if applicable). However, for

participants who are scheduled to start the intervention phase more than 2 weeks after the baseline visit, the C-SSRS, IDSSR, and PCL-5 will be readministered within 1 week prior to start of intervention.

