Differences in functional connectivity between Veterans with STBs and controls.

These analyses test the hypothesis that the VMPFC-to-striatal decision-making circuit is less functionally cohesive in Veterans with STBs. Functional connectivity analyses of both task (reward expectancy) and resting-state will be conducted using the CONN Toolbox.⁵⁰

Unsmoothed residual BOLD time courses will be extracted from each subjects' preprocessed data and then cross-correlated. The resulting correlations will be converted to z-scores via Fisher's R-to-Z transformation in order to improve conformation to the assumptions of the GLMs used for seed-based hypothesis testing. Z-scores will be entered into GLMs comparing VMPFC-to-striatal connectivity between groups. For task-based functional connectivity, a weighted GLM approach will be used to compare connectivity during the expected reward and prediction error task conditions of between Veterans with and without STBs. Additional analyses using ROIs functionally-defined in the univariate analysis described above as seeds may also be run.

Design Considerations & Alternative Outcomes: This hypothesis testing sequence focuses on the VMPFC-to-striatum decision-making circuit. However, effects may be mediated by regions outside this *a priori* network e.g. in the amygdala-to-VMPFC circuit implicated in bipolar disorder with suicidality [85]. The role of this circuit could be explored should we fail to reject the null hypothesis. Alternatively, a data-driven method such as multi-voxel pattern analysis could be used to functionally identify neural circuits differing between Veterans with and without STBs.

E3.2 Evaluate whether correlates of decision-making and cognitive control indicate risk severity.

Hypotheses: Decision-making will be less risky and/or impulsive in higher- vs. lower- risk Veterans with STBs. Structural and functional integrity of cognitive control regions will be superior in higher-risk Veterans with STBs.

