Rationale: Studies comparing decision-making between individuals who have made high-risk (well-organized, highly lethal) attempts vs. those making less organized or less medically serious attempts have found that decision-making is less impulsive in higher- risk attempters [86]. In fact, decision-making in high-risk attempters is even less impulsive than it is in healthy controls. Some propose that the capacity to make a serious suicide attempt develops alongside the ability to inhibit prepotent pain and fear responses associated with death [87]. Thus, paradoxically, greater inhibitory cognitive control may facilitate development of suicidal behavior. As a test of this hypothesis, we will compare behavioral and functional neuroimaging data collected during the SSRT, an inhibitory cognitive control task, between high- and lower-risk Veterans with STBs. We will also examine associations between suicide and other cognitive control measures to assess the specificity of the link between attempts and inhibitory control. to assess the specificity of the link between attempts and inhibitory control.

Participant groups: The high-risk group will be comprised of Veterans with history of suicide attempt (up to n=30), while the low-risk group will include Veterans with ideation only (up to n=30). See alternative methods for risk grouping in the Design Considerations section below. Diagnosis matched controls (up to n=60) are also used in some analyses.

Data sources: Structural data (cortical thickness and volume) and diffusion MRI data. FMRI data used in Aim 2 analyses will come from either the SSRT, the scanned decision-making task, or resting state runs. Behavioral measures of decision-making include data from the scanned decision-making task. Behavioral measures of cognitive control include data from the scanned SSRT, and the un-scanned Intra-Dimensional Card Sort and Flanker tasks.

General statistical details: Age and sex will be treated as covariates of no interest in all statistical analyses. Intracranial volume (computed by Freesurfer) will also be used as a nuisance covariate in morphometry analyses to control for size-related variance. Residual effects of motion on functional connectivity estimates will be tested post hoc by regressing individuals' frame-to- frame motion against functional connectivity beta values ⁵⁵. Potential effects of impulsivity, depression, anxiety, and sleep on outcomes will be explored in post hoc sensitivity analyses.

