Design considerations & alternative strategies for Aim 2. This design uses a categorical factor to define groups that approximates risk by history of attempt versus ideation, based on the strength of previous attempt as a risk factor for subsequent attempts. While straight-forward, we acknowledge that within-group heterogeneity may invalidate this grouping strategy. For instance, the ideation group could contain a significant number of Veterans with highly detailed suicide plans that have begun obtaining means that would be better classified as high-risk. In recognition of this issue, we will also compute empirically-determined risk categorization thresholds based on Beck Lethality Scale, Suicide Intent Scale, and Scale for Suicide Ideation scores. Alternatively, we may use continuous variables operationalizing suicidal planning, intent, or lethality for these analyses.

E3.3 (Exploratory) Integrate EHR data and neurocognitive markers into predictive models of STBs.

We will combine EHR data and objective cognitive measures forming a high-dimensional, multi-modal dataset. Machine learning algorithms will be applied to examine the predictive utility of this approach.

Rationale: Machine learning algorithms can accommodate large predictor sets and can model complex interactions among factors. Models built on EHR outperform traditional models with predictive accuracy in excess of AUC +0.70. We will subject an EHR dataset enriched with additional, objective, cognitive measures of suicidality (defined in Aims 1 & 2) to machine learning classification. Three types of supervised machine learning models (described below) will be used for this exploratory analysis. Models will be constructed both with, and without, Aim 1 & 2 measures to test if their inclusion improves suicide prediction.

Data sources: Aggregated EHR data (Section D6.2) and subject-level performance outcomes on the reward expectancy scanned task, Delay Discounting task, Iowa Gambling Task, Flanker Task, Dimensional Card Sort Task, and SSRT task.

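### E3.2 and E3.3 list behavioural data from the scanned card-guessing task, which cannot measure risky or impulsive choice; E3.2 should instead test Monetary-Choice and Iowa Gambling scores directly between risk groups

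*Combined protocol and SAP*

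**What the plan says.** **The task (D4.3.4e, II. Reward expectancy task).** "The task is divided into two, 48 trial, 7-minute scanner runs". On each trial the participant first bets by button press "whether the number on the next card displayed (range=1-9) will be higher or lower than 5". Then comes the cue: "Next, an expectancy card is shown communicating the likelihood that the bet will result in a win, a loss, no change", or that a win and a loss are equally likely. The number follows, then the amount won or lost. The section describes no choice after the cue. On the schedule it says "Trial order is randomized with 12 trials per category (win, loss, neutral, ambiguous" and "Expectancy cues are accurate on 50% of trials (except for neutral trials". The stated purpose is to locate brain areas that process reward and expected value.

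**Its behavioural use.** E3.1 lists card guessing as the scanned decision-making task, alongside the unscanned Iowa Gambling and Monetary-Choice tasks. The first E3.2 hypothesis is "Decision-making will be less risky and/or impulsive in higher- vs. lower- risk Veterans with STBs", and the E3.2 data sources say "Behavioral measures of decision-making include data from the scanned decision-making task". The other two tasks are not named there. The E3.3 data sources include "subject-level performance outcomes on the reward expectancy scanned task". The plan defines no behavioural score for the card task.

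**The E3.2 analyses.** The behavioural section of E3.2 has entries for the Card Sort and the Flanker only. The Flanker entry describes winnings and a ratio of high- to low-risk gambles, which are the scores that E3.1 gives to the Iowa Gambling Task. Further on, under the heading on adaptive decision-making and inhibitory control, GLMs predict Monetary-Choice discounting or the Iowa Gambling proportion of risky choices. Their predictors are group (high-risk, low-risk, controls) together with stop-signal reaction time, an impulsivity score or inhibition-related activation.

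**The concern.** A measure can test a hypothesis about risky or impulsive choice only if participants can choose more or less riskily, or more or less impulsively. The card task gives them no such option, yet it is the only decision-making task named in the E3.2 data sources.

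The two tasks in the same visit battery that do offer such choices (D4.3.2) appear in E3.2 only in models that also hold a term for inhibition, impulsivity or activation. The plan's own account is that superior inhibitory control enables less impulsive choice. A group coefficient adjusted for inhibition therefore estimates what is left after part of the proposed pathway has been removed. It does not estimate the difference that the hypothesis asserts.

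At stake is whether E3.2 can answer its first hypothesis as worded. In E3.3, an analyst would have to invent a card-task score after the data are in.

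**Working it through.** **1. Schedule.** Four cue categories x 12 trials = 48, which reproduces the stated trials per run.

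**2. Can a bet be risky or impulsive?** On a fair deck numbered 1 to 9:
- A high bet wins on 6, 7, 8 or 9, so P(win) = 4/9. It loses on 1 to 4, so P(loss) = 4/9. A 5 leaves P = 1/9.
- A low bet is the mirror image: 4/9, 4/9 and 1/9.

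For any fixed win and loss amounts, both bets have the same mean and the same spread, so neither is the riskier. Both pay at the same point in the trial, so neither is the more impatient. This step uses only the D4.3.4e description and carries the main conclusion.

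**3. Does the result depend on the bet at all?** Probably not, but this is inferred.
- E3.1 sets the expected values at +0.5 (probable win), -0.375 (probable loss), +0.125 (ambiguous) and 0 (neutral).
- Suppose an accurate cue pays the cued amount and a misleading one pays nothing. Then win = 0.5/0.5 = +1 and loss = -0.375/0.5 = -0.75. The ambiguous value is 0.5 x 1 + 0.5 x (-0.75) = +0.125, which matches.
- If misleading cues reversed the result instead, win and loss cues would share one expected value, contrary to E3.1.
- A randomly drawn deck would give 48/9 = 5.3 fives per run on average. With 12 neutral trials per run, the binomial probability of 12 or more fives is 0.005.

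The number shown therefore seems to be chosen to fit the cue category. The stakes of +1 and -0.75 are back-solved and are not stated in the plan.

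**4. What tests the E3.2 hypothesis?**

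| Place in E3 | Card task | Monetary-Choice | Iowa Gambling |
|---|---|---|---|
| E3.2 data sources, decision-making behaviour | named | not named | not named |
| E3.2 behavioural section | no test | no test | its scores, under the Flanker heading |
| E3.2 GLMs | not an outcome | outcome, with a further term | outcome, with a further term |
| E3.3 predictors | named, score undefined | named | named |

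**5. What a direct test could detect.** Assume the maximum 30 high-risk and 30 low-risk Veterans, two covariates and two-sided alpha of 0.05.
- df = 60 - 4 = 56, and critical t = 2.003.
- Noncentrality = d x sqrt(30 x 30/60) = d x 3.873.
- d = 0.5: noncentrality 1.94, power 48%.
- d = 0.8: noncentrality 3.10, power 86%.

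These figures describe the proposed test, not the defect.

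**The case against.** **The data-source sentence is not exhaustive.** It says that measures include the scanned task, and no E3.2 model takes a card-task score as its outcome. This stands. A reader might infer that the hypothesis rests on the card task, so that a null result there would count against it. The documents do not support that, because the specified models predict Monetary-Choice and Iowa Gambling scores with group among the predictors.

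**A group test may already exist.** The sentence under the Flanker heading is very likely the Iowa Gambling ANCOVA, misplaced. E3.1 also enters both tasks' scores into ANCOVAs of group differences, and its power statement is for three groups. That statement reproduces: with f = 0.4 and N = 72, lambda = 0.16 x 72 = 11.52, and power is 0.853 against the stated 85%. This stands in part. However, E3.1's hypothesis is suicidality against none. Its groups are defined by the reason for hospitalisation, while E3.2 groups by history of attempt. E3.2 still has no Monetary-Choice test that omits the further term.

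**Card-task behaviour could differ between people.** Reaction time, omissions or switching after a loss might separate the groups. That is true, so a reader who infers that any card-task score has only chance power goes too far. But none of these scores is specified, and none measures riskiness.

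**Fixed winnings.** A reader might also infer that every participant ends with the same winnings. That needs the back-solved stakes and exactly 50% accuracy within each cue type. If 50% is a probability, totals vary by chance.

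**E3.3 is exploratory.** It is, and no material loss of classification accuracy has been shown.

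**Conclusion.** The point holds in a limited form. The higher/lower bet cannot measure risky or impulsive choice. That follows from the task description alone, without any assumption about stakes or a fixed schedule. That outcomes are also independent of the bet is a reasonable inference from D4.3.4e and the E3.1 values, not a stated fact.

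The consequences are of two kinds:
- In E3.2 the data sources and the models do not match, and the direct contrast that the first hypothesis calls for is not clearly specified. The GLMs address a related question, with part of the proposed pathway held constant.
- In E3.3 one listed predictor has no definition and no clear meaning.

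Both sit in secondary or exploratory imaging analyses, and the treatment comparison is untouched. A reader might go on to infer that the E3.1 imaging results are mislabelled or invalid. The documents do not support that: the expectancy and prediction-error regressors model responses to cue and feedback, which is what the task is designed to elicit. What to call those responses is a matter of terminology.

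**What to change.** 1. **E3.2 data sources.** Name the Monetary-Choice discounting rate and the Iowa Gambling proportion of high-risk selections as the behavioural decision-making measures, and remove the card task from that sentence.
2. **E3.2 behavioural analysis.** Compare each measure between high- and low-risk Veterans by ANCOVA with age and sex, without the inhibition, impulsivity or activation term. Keep the existing GLMs as follow-up on the pathway. Report confidence intervals, because a medium difference could easily be missed at 30 v 30.
3. **Flanker entry.** Move the winnings and gamble sentence to the Iowa Gambling Task, and give the Flanker its own scores.
4. **E3.3 data sources.** Drop the card-task behavioural score, or replace it with that task's ROI responses. The latter would fit the A5 hypothesis, which merges brain, cognitive and EHR data.
5. **fMRI.** Leave the task and its imaging models unchanged.

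The cost is plan wording and two extra ANCOVAs on data already collected at the MRI visit. No new procedure or participant burden is involved.
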